7.4. Analysis of Secondary Efficacy Parameters (Phase 2)

7.4.1. Ordinal Categorical Response Score

The ordinal response scores are defined as the following:

- 1 = CR per irRECIST v1.1
- 2 = Very good response, defined as > 60% tumor reduction
- 3 = Minor response, defined as >30% to $\leq 60\%$ tumor reduction
- 4 = SD per irRECIST v1.1
- 5 = PD per irRECIST v1.1

The frequency of subjects in each category will be summarized by treatment group.

7.4.2. Duration of Response

For objective responders, the DoR is the time from the first overall response contributing to an objective response (CR or PR) to the earlier of the subject's death or first overall response of PD (by irRECIST v1.1 for selected solid tumors and the modified Lugano Classification for DLBCL) occurring after the first overall response contributing to the objective response. Median DoR and CIs will be estimated using the Kaplan-Meier method. Subjects who are still responding at the time of database freeze or discontinuation will be right-censored at the last valid response assessment date before starting any new anticancer therapy. The DoR evaluation will be performed separately for each treatment group and no statistical comparison will be made.

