#### 9.4.2. Secondary Analyses

Secondary efficacy analysis will be conducted for the efficacy evaluable population.

Progression-free survival is defined as number of days from the first day of taking study drug to the earlier of death or disease progression by irRECIST v1.1 for select solid tumors and modified Lugano Classification (Cheson et al 2014) for DLBCL. Time-to-event data will be analyzed by the Kaplan-Meier method, treating subjects with no observed death or progression as censored at

their last valid response assessment or last valid response assessment date prior to post study cancer treatment. For the OS analysis, the nonparametric Kaplan-Meier method will be used to estimate the survival time distribution and the median survival of each tumor type.

For objective responders, the duration of response is the time from the first objective response contributing to an objective response, to the first objective response of PD (by irRECIST v1.1) occurring after the first objective response contributing to the objective response. Median duration of response will be estimated using the Kaplan-Meier method. The duration of disease control is the time from the treatment start date to the first objective response of PD (by irRECIST v1.1 or Lugano Classification ([Cheson et al 2014](#)) occurring after the first objective response of CR/PR/SD. Median duration of disease control will be estimated using the Kaplan-Meier method.

The ordinal response scores are defined as the following:

- 1 = Complete response per irRECIST v1.1
- 2 = Very good response, defined as > 60% tumor reduction
- 3 = Minor response, defined as >30% to ≤ 60% tumor reduction
- 4 = Stable disease per irRECIST v1.1
- 5 = Progressive disease per irRECIST v1.1

The frequency of subjects in each category will be summarized by tumor type.

For OS analysis, the Kaplan-Meier method will be used to estimate the survival time distribution and the median survival of each tumor type.

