2.3.2. Secondary Endpoints (Phase 2)

- Ordinal categorical response score, determined by radiographic disease assessments per irRECIST v1.1. The 5-category ordinal response endpoint is determined at a given timepoint by classifying response into one of the following groups: CR; very good response, defined as partial response (PR) with percent reduction from baseline in tumor line length > 60%; minor response, defined as PR with percent reduction from baseline in tumor line length > 30% to ≤ 60%; SD; and PD.
- Duration of response determined by radiographic disease assessment defined as the time from earliest date of disease response until earliest date of disease progression.
- Progression-free survival determined from treatment start date until first date for confirmed disease progression or death.
- Duration of disease control (including CR, PR, and SD) measuring from treatment start date until the earliest date of disease progression for subjects whose best response is SD or better.
- Overall survival determined from the date of first dose until death due to any cause.
- Safety and tolerability of the treatment regimens through assessment of AEs and changes in safety assessments, including laboratory parameters.

[figure not shown]

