7.4.3. Progression-Free Survival

Progression-free survival is defined as the number of days from the date of first dose (which is not necessarily Day 1) to the earlier of death or disease progression by irRECIST v1.1 for selected solid tumors and the modified Lugano Classification for DLBCL. Date of death will be determined using the Death Report, the Survival Follow-Up, and the Subject Status eCRFs. Disease progression is defined as progression confirmed by a second, consecutive assessment at least 4 weeks apart with the option for continuing treatment while awaiting radiologic confirmation of progression. Censoring for PFS will follow the algorithm outlined in Table 6, which is based on FDA guidance (FDA 2007). Note that the Protocol mandates radiological evaluation of subjects every 9 weeks for the first 18 months and then may be done every 12 weeks thereafter. The analyses will be based on the efficacy evaluable population, according to treatment assignment. Time-to-event data will be analyzed by the Kaplan-Meier method.

Situation	Outcome	Date of Progression or Censoring
No baseline tumor assessments	Censored	Treatment start date
Progression documented between scheduled visits	Progressed	 Earliest of: Date of radiological assessment showing new lesion (if progression is based on new lesion); or Date of last radiological assessment of measured lesions (if progression is based on increase in sum of measured lesions)
No progression	Censored	Date of last valid radiologic assessment (not NE and not missing)
Treatment discontinuation for undocumented progression	Censored	Date of last valid radiologic assessment (not NE and not missing)
Treatment discontinuation for toxicity or other reason	Censored	Date of last valid radiologic assessment (not NE and not missing)
New anticancer treatment started	Censored	Date of last valid radiologic assessment (not NE and not missing)
Death before first PD assessment	Progressed	Date of death
Death between adequate assessment visits	Progressed	Date of death
Death or progression after more than 1 missed assessment	Censored	Date of last valid radiologic assessment (not NE and not missing)

Table 6: Evaluation and Censoring of Progression-Free Survival

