7.4.4. Duration of Disease Control

The duration of disease control is the time from the first dose date to the first objective response of PD (by irRECIST v1.1 or modified Lugano Classification [Cheson et al 2014]), death, or last tumor assessment date (if PD/death not present), for subjects with best overall response of SD or better. In the case of SD, measurements must meet the SD criteria at least once after study entry at a minimum interval of 56 days. Median duration of disease control and CIs will be estimated using the Kaplan-Meier method. Subjects who have SD or better at the clinical data cutoff or discontinuation will be right-censored at last valid response assessment date before starting any new anticancer therapy. The duration of disease control evaluation will be performed separately for each treatment group and no statistical comparison will be made.

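### Duration of response and of disease control: SAP 7.4.2 and 7.4.4 count death as an event, the Protocol and SAP 2.3.2 do not, the departure is undeclared, and the PD confirmation rule is not cross-referenced

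*SAP*

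**What the plan says.** **Duration of response.** The SAP's endpoint section describes it as "defined as the time from earliest date of disease response until earliest date of disease progression"; Protocol 4.2.2 uses the same definition. Protocol 9.4.2 runs it "to the first objective response of PD (by irRECIST v1.1) occurring after the first objective response contributing to the objective response". None of these mentions death. The SAP's methods section, 7.4.2, runs it "to the earlier of the subject's death or first overall response of PD".

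**Duration of disease control.** SAP 2.3.2 measures it "until the earliest date of disease progression for subjects whose best response is SD or better". Protocol 9.4.2 says: "The duration of disease control is the time from the treatment start date to the first objective response of PD". Again there is no death. SAP 7.4.4 adds further end points to PD: "death, or last tumor assessment date (if PD/death not present").

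**PFS, for comparison.** The endpoint lists in both documents name confirmed progression or death. SAP 7.4.3 repeats the confirmation requirement: "Disease progression is defined as progression confirmed by a second, consecutive assessment at least 4 weeks apart".

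**Confirmation in general.** SAP 7.3.1 requires a PD under irRECIST to be confirmed, sets out when an unconfirmed PD is nevertheless counted as confirmed, and closes by making a confirmed PD an event. Sections 7.4.2 and 7.4.4 do not refer to it.

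**Change log.** SAP 10.1 records that analyses were reduced for the abbreviated report. SAP 10.2.4 says in general terms that unclear sections were remedied. Neither mentions adding death to these two endpoints.

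**The concern.** There are two separate issues.

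The first is death. Under a progression-only definition, a responder who dies without PD has no event and would ordinarily be censored. Death in a responder is plausibly related to the disease or its treatment, so that censoring is informative and lengthens the Kaplan-Meier median. The SAP's endpoint section and its methods section therefore describe two different quantities under one name. A report that takes its definition from 2.3.2 and its numbers from 7.4.2 would mislabel the result.

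The second is which PD stops the clock. SAP 7.3.1 and its Table 5 use overall response for the reading at a single assessment. Section 7.4.2 stops at the first such reading of PD, and 7.4.4 uses similar wording. Protocol 7.6.3.1 foresees a first PD followed by a repeat scan showing SD, PR or CR, with treatment continuing. Taken literally, 7.4.2 ends that subject's DoR at the first PD while PFS carries on.

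Both are secondary endpoints kept in the abbreviated report. They are tabulated by cohort and by PD-L1 status or TPS, so the groups are small.

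**Working it through.** The plan states no expected median, event count or power for either endpoint, so there is no figure to reproduce. The check is a comparison of texts, followed by an illustration of size.

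**Step 1: event definitions side by side**

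| Place | DoR ends at | Disease control ends at |
|---|---|---|
| Protocol 4.2.2; SAP 2.3.2 | progression | progression |
| Protocol 9.4.2 | PD | PD |
| SAP 7.4.2; 7.4.4 | PD or death | PD or death |

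The lists in Protocol 4.2.2 and SAP 2.3.2 do name death for PFS, so its absence for the other two endpoints reads as a difference and not as shorthand.

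**Step 2: confirmation**

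- SAP 7.3.1 states the confirmation rule for irRECIST PD without limiting it to PFS. Its closing statement about events can only serve time-to-event endpoints, because ORR has none.
- SAP 7.4.2 and 7.4.4 define PD by irRECIST, so the rule can be read into them.
- The Protocol synopsis (Study Schedule/Procedures) defines disease progression generally as confirmed.
- Protocol 7.6.3.1 says that if a PD is not confirmed and treatment continues, the progression date comes from the next PD that is itself confirmed. Protocol 7.6.4 carries the adaptation over to Lugano.
- On the other side, the endpoint lists attach confirmation to PFS alone, 7.4.3 restates it for PFS alone, and the wording of 7.4.2 matches the single-assessment term of Table 5.

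The intended PD is therefore most likely the confirmed one, but 7.4.2 and 7.4.4 do not say so.

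**Step 3: size of the death rule (assumed inputs)**

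Let PD have constant hazard λ and death without PD constant hazard δ, acting independently.

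- Median with PD only, deaths censored: ln 2 / λ
- Median with PD or death: ln 2 / (λ + δ)
- Share of first events that are deaths: s = δ / (λ + δ)
- Ratio of the second median to the first: λ / (λ + δ) = 1 − s

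For an assumed PD-only median of 12 months:

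| s | Median with death counted (months) |
|---|---|
| 5% | 12 × 0.95 = 11.4 |
| 10% | 12 × 0.90 = 10.8 |
| 20% | 12 × 0.80 = 9.6 |
| 30% | 12 × 0.70 = 8.4 |

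**Step 4: how many responders**

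From SAP Table 4, at full planned enrollment and under the alternative, expected responders run from 27 × 0.20 = 5.4 (primary refractory melanoma) to 42 × 0.56 = 23.5 (NSCLC PD-L1 high), that is, about 5 to 24 per cohort. Protocol Table 3 marks several cohorts, including both of these, as discontinued before full enrollment, so actual numbers may be lower. In the smallest case one death is 1 / 5.4, or about 19%, of expected responders.

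**Step 5: direction of the confirmation effect**

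A confirmed PD cannot be dated earlier than the first PD reading. Against a literal reading of 7.4.2, requiring confirmation therefore leaves DoR unchanged or lengthens it. No size is computed, because the documents give no rate of unconfirmed PD.

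**The case against.** **The methods section governs.** SAP 7.4.2 and 7.4.4 are explicit and agree with each other, while SAP 2.3.2 merely repeats the Protocol's endpoint text. A programmer working from section 7.4 has one death rule. This limits the practical risk, but the SAP still contradicts itself, and its departure from the Protocol is not declared.

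**The Protocol never says deaths are censored.** That is correct. A reader might infer that it prescribes this, but the censoring is only the usual consequence of a PD-only definition. Protocol 9.4.2 analyzes time-to-event data "treating subjects with no observed death or progression as censored at" the last valid assessment, which would not censor deaths. That sentence stands in the PFS paragraph, however, and the definitions of DoR and disease control that follow it still name PD alone. It adds to the uncertainty and does not settle it.

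**PD is already defined as confirmed.** A reader might infer that the SAP holds a second, unconfirmed PD definition for DoR and disease control. The documents do not support this: SAP 7.3.1, the Protocol synopsis and Protocol 7.6.3.1 and 7.6.4 all point to confirmed PD. What remains is a missing cross-reference and a term that invites the other reading.

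**These are secondary, descriptive endpoints.** They are estimated within groups, without statistical comparison, for an abbreviated report. That bears on priority. It does not remove the inconsistency.

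**Conclusion.** The conflict over death is established. The Protocol's definitions and SAP 2.3.2 end both endpoints at progression, SAP 7.4.2 and 7.4.4 add death, and SAP 10.1 and 10.2 do not name the change. The two rules give different medians whenever a subject dies without PD.

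The confirmation point holds only as an ambiguity: the rule exists in 7.3.1, but 7.4.2 and 7.4.4 do not invoke it.

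The 5% to 30% shortening rests on assumed death shares and on independent exponential hazards. It shows the mechanism and does not predict this trial's result. The documents support no particular figure, and larger effects obtained by choosing higher death hazards would have no better basis. The conclusion on ORR does not depend on any of this. The point should be corrected, but it does not threaten the primary analysis.

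**What to change.** - In SAP 2.3.2, 7.4.2 and 7.4.4, define the event as whichever comes first: death, or the first PD counted as confirmed under 7.3.1. Use the progression date already derived for PFS. Keep the start points as they are: first CR or PR for DoR, first dose for disease control.
- State that the 7.3.1 rule also applies to modified Lugano in DLBCL, since 7.3.1 is worded for irRECIST only.
- State whether the Table 6 rule, which censors PFS when death or progression follows more than one missed assessment, also applies to DoR and disease control. Without this, the endpoints could still end differently in the same subject even with a common PD date.
- Record the departure from Protocol 4.2.2 and 9.4.2 in SAP 10.1.

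The cost is wording, and the derivation reuses an existing date. Relative to a PD-only rule, durations stay the same or shorten because deaths count. Relative to 7.4.2 read literally, where deaths already count, confirmation leaves DoR the same or lengthens it.

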7.4.3. Progression-Free Survival

Progression-free survival is defined as the number of days from the date of first dose (which is not necessarily Day 1) to the earlier of death or disease progression by irRECIST v1.1 for selected solid tumors and the modified Lugano Classification for DLBCL. Date of death will be determined using the Death Report, the Survival Follow-Up, and the Subject Status eCRFs. Disease progression is defined as progression confirmed by a second, consecutive assessment at least 4 weeks apart with the option for continuing treatment while awaiting radiologic confirmation of progression. Censoring for PFS will follow the algorithm outlined in Table 6, which is based on FDA guidance (FDA 2007). Note that the Protocol mandates radiological evaluation of subjects every 9 weeks for the first 18 months and then may be done every 12 weeks thereafter. The analyses will be based on the efficacy evaluable population, according to treatment assignment. Time-to-event data will be analyzed by the Kaplan-Meier method.

Situation	Outcome	Date of Progression or Censoring
No baseline tumor assessments	Censored	Treatment start date
Progression documented between scheduled visits	Progressed	 Earliest of: Date of radiological assessment showing new lesion (if progression is based on new lesion); or Date of last radiological assessment of measured lesions (if progression is based on increase in sum of measured lesions)
No progression	Censored	Date of last valid radiologic assessment (not NE and not missing)
Treatment discontinuation for undocumented progression	Censored	Date of last valid radiologic assessment (not NE and not missing)
Treatment discontinuation for toxicity or other reason	Censored	Date of last valid radiologic assessment (not NE and not missing)
New anticancer treatment started	Censored	Date of last valid radiologic assessment (not NE and not missing)
Death before first PD assessment	Progressed	Date of death
Death between adequate assessment visits	Progressed	Date of death
Death or progression after more than 1 missed assessment	Censored	Date of last valid radiologic assessment (not NE and not missing)

Table 6: Evaluation and Censoring of Progression-Free Survival

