7.3. Analysis of the Primary Efficacy Parameter

7.3.1. Primary Efficacy Analysis

The primary variable for the Phase 2 expansion portion of the study is ORR, which is defined as the proportion of subjects with best overall response (CR or PR) by irRECIST v1.1 for select solid tumors and modified Lugano Classification (Cheson et al 2014) for DLBCL. Subjects' overall response will be evaluated as CR, PR, SD, PD, or not evaluable (NE) at each postbaseline radiological assessment based on changes in target lesions, nontarget lesions, and appearance of new lesions. The best overall response will be determined from response assessments before and including the date of starting new anticancer therapy. If any alternative cancer therapy is taken while on study, any subsequent assessments will be excluded from the best overall response determination.

For subjects with measurable disease at baseline, the irRECIST version 1.1 assessment criteria presented in Table 5 can be used to determine the overall response at a given timepoint based on the target lesion, nontarget lesion, and new lesion assessment.

Target Lesions	Nontarget Lesions	New Lesions	Overall Response
CR	CR	No	CR
CR	Non-CR / Non-PD	No	PR
CR	NE	No	PR
PR	Non-PD or NE	No	PR
SD	Non-PD or NE	No	SD
Not all evaluated	Non-PD	No	NE
PD	Any	Yes or No	PD
Any	PD	Yes or No	PD
Any	Any	Yes	PD

Table 5: irRECIST for Overall Response: Measurable Disease at Baseline

A subject is considered an objective responder as assessed by irRECIST if they have an overall response of CR or PR at any postbaseline visit. The proportion of responders within each treatment group will be estimated with 90% confidence intervals (CIs) by treatment group. Confidence intervals will be calculated based on the Clopper-Pearson method for binomial distributions. Within each treatment group, 1 sample binomial test will be used to test the null hypothesis.

Using irRECIST criteria, a PD needs to be confirmed as follows.

For each PD, if there is a second PD on the first response assessment that was \geq 4 weeks after the PD, then the PD is defined as confirmed, and the date of progression is the date of the first PD. Otherwise the PD is defined as unconfirmed.

If a subject had an unconfirmed PD, and there are no valid response assessments after that PD (not NE or missing), then the PD will be counted as follows:

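### When new anticancer treatment starts, SAP Table 6 censors PFS at the last valid scan without limiting it to scans before that treatment, unlike Protocol 9.4.2 and the SAP's own rules for DoR and disease control

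*SAP*

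**What the plan says.** **PFS, Protocol 9.4.2.** Subjects with no observed death or progression are censored at their last valid response assessment, or at the "last valid response assessment date prior to post study cancer treatment".

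**PFS, SAP 7.4.3, Table 6.** The row "New anticancer treatment started" has outcome censored. Its date cell begins "Date of last valid radiologic assessment (not NE and not missing" and adds no other condition. The rows for no progression, and for stopping treatment because of toxicity or another reason, use the same date wording.

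**Duration of response, SAP 7.4.2.** Subjects still responding at database freeze or discontinuation are "right-censored at the last valid response assessment date before starting any new anticancer therapy".

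**Duration of disease control, SAP 7.4.4.** Subjects with SD or better at data cutoff or discontinuation are "right-censored at last valid response assessment date before starting any new anticancer therapy".

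**Best overall response, SAP 7.3.1.** "If any alternative cancer therapy is taken while on study, any subsequent assessments will be excluded from the best overall response determination".

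**Confirmation of progression, SAP 7.3.1.** A PD is confirmed "if there is a second PD on the first response assessment that was" at least 4 weeks later; otherwise it is unconfirmed. New therapy is not mentioned. A fallback then counts some unconfirmed PDs as confirmed. Its lead-in restricts it to subjects with no valid assessment after the PD. Its first bullet covers subjects who stopped both drugs, or left the study, ahead of a later valid assessment.

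SAP 10.1 and 10.2, which list changes from the Protocol and between SAP versions, record no change to PFS censoring.

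**The concern.** A row for new treatment is useful only if it stops follow-up when that treatment starts. With the same date as the no-progression row, it does not. Any later scan in the database moves the censoring date into the period on the next therapy. Because the row's outcome is censored, that extra period can add only event-free time at risk, so the Kaplan-Meier PFS curve can move only upwards.

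The SAP includes the limit for the two neighbouring time-to-event endpoints and for best overall response, and the Protocol includes it for PFS. A programmer following Table 6 would therefore depart from the Protocol without any recorded decision to do so, and could give one subject different cutoffs for PFS and disease control. PFS is retained in the abbreviated report: SAP 10.1 keeps the secondary endpoints, and Appendix E plans PFS tables for every Phase 2 tumor type.

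The confirmation rule raises a related question. If a subject has a PD, stops both drugs, starts new therapy and then has a scan that is not PD, 7.3.1 does not say clearly whether the PD still counts.

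**Working it through.** There is no stated figure to reproduce. The check applies the rules to two hypothetical subjects and then sizes the effect under stated assumptions. Scan days 63 and 126 are Weeks 9 and 18 in Protocol 7.6.2.

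**Subject A: SD at day 63, new therapy at day 80, SD at day 126, no death.**

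| Rule | Censoring day |
|---|---|
| PFS, SAP Table 6 as written | 126 |
| PFS, Protocol 9.4.2 | 63 |
| Disease control, SAP 7.4.4 | 63 |

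Day 63 also meets the 56-day minimum that 7.4.4 sets for SD. The PFS difference is 126 − 63 = 63 days, of which 126 − 80 = 46 are on the next therapy.

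**Subject B: PD at day 63, both drugs stopped, new therapy at day 80, SD at day 126.**

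- If the lead-in of the fallback governs: a valid later scan exists, the fallback is closed, the PD is unconfirmed, and PFS is censored at day 126.
- If the first bullet governs: both drugs were stopped before the later scan, so the PD counts at day 63.
- If scans after new therapy are ignored: no valid scan follows the PD, the fallback applies, and the PD counts at day 63.

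The text supports either of the first two readings. With no scan at day 126, the PD would be counted at day 63 without dispute.

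**Size, Table 6 cell.** Assume a cohort of 32 with 16 PDs at day 63, 6 at day 126, 4 at day 210 and 6 subjects with no event. Let k of those 6 have Subject A's history.

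- As written, all 16 subjects without PD at day 63 are at risk at day 126: S(126) = (16/32) × (1 − 6/16) = 31.25%.
- With the limit, k leave at day 63: S(126) = (16/32) × (1 − 6/(16 − k)).
- k = 1: 0.5 × 9/15 = 30.0%, a difference of 1.25 points.
- k = 2: 0.5 × 8/14 = 28.6%, a difference of 2.7 points.

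The binomial standard error is √(0.3125 × 0.6875/32) = 8.2 points. This places every affected subject in one interval with many events; a more spread-out pattern gives less.

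**Size, confirmation ambiguity, if resolved against counting the PD.** Assume exponential PFS with median 120 days and n = 36. The share progressed by day 126, the last scheduled scan before six months, is 1 − 2^(−126/120) = 51.7%. If 2%, 5% or 10% of those PDs were left unconfirmed, six-month PFS would rise by at most 0.517 × 2%, 5% or 10%, that is 1.0, 2.6 or 5.2 points. The standard error is √(0.483 × 0.517/36) = 8.3 points. These percentages are assumptions.

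**The case against.** The strongest reply is that this is a drafting slip with little reach. Table 6 gives new treatment its own censored row, so a cut was probably intended. Protocol 7.6.2 ends study imaging at the start of new anticancer treatment. The follow-up imaging in Protocol 6.4.2 had the same endpoint and was withdrawn by Amendment 10. PFS is secondary and summarized descriptively in non-randomized cohorts.

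Most of that stands, and it limits the size. It does not make the cell right, and exposure is not nil. Protocol Tables 10 and 16 ask for a repeat scan where possible after unstable subjects stop treatment, although 7.6.3.1 does not require it. The discontinuation scan in Table 12 has a 4-week window, and 6.4.1 foresees new therapy within 42 days of the last dose. SAP 7.3.1 provides for assessments after alternative therapy, but only conditionally, so it does not show that such scans are expected.

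A reader might infer three stronger points that the documents do not support:

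- *That a subject who progresses on the next therapy shows the conflict.* The Protocol limit covers only subjects with no observed death or progression. The DoR and disease-control limits likewise cover subjects still responding, or with SD or better, at cutoff or discontinuation. Read literally, the Protocol could count that progression as an event, so this case does not show the SAP departing from it.
- *That the confirmation rule contradicts the Protocol.* Protocol 7.6.3.1 has no new-therapy limit for confirming PD either. This is a gap in both documents.
- *That the SAP cancels real progressions.* The first bullet of the fallback can be read as keeping the PD. The lead-in points the other way, so the text is ambiguous.

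**Conclusion.** The point holds for the Table 6 cell. As written, it departs from Protocol 9.4.2 for subjects without an event and from the SAP's own treatment of DoR and disease control, with no recorded intention to change. Its direction is fixed: PFS can only look longer. The confirmation rule in 7.3.1 needs clarifying, but it is an ambiguity and not a demonstrated error.

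The number affected is probably small, and the documents give no rate. Under the assumed cohort, one or two affected subjects in 32 shift PFS at day 126 by about 1.3 or 2.7 points against a standard error of about 8. A claim that PFS results would be materially misleading is therefore not supported. ORR is not affected, because best overall response already excludes assessments after alternative therapy. The correction is still worthwhile: it removes a one-directional bias and gives the endpoints a common cutoff.

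**What to change.** 1. In SAP Table 6, new-treatment row, limit the date to the last valid radiologic assessment *before the start of new anticancer treatment*, keeping the exclusion of NE and missing assessments.
2. In SAP 7.3.1, reconcile the fallback's lead-in with its first bullet by stating that assessments after the start of new anticancer therapy neither confirm nor refute a PD. A PD in a subject off both drugs with no valid scan between it and the new therapy then counts at its own date.

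The first change restores the Protocol's rule for subjects without an event. The second is a clarification that neither document now contains and should be recorded as such in SAP Section 10. The cost is a few words and the matching programming; PFS may become slightly shorter.
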